 - Note 2: If a sufficient amount of tissue is not available, a fresh biopsy may be taken, provided the procedure is not deemed high-risk and is clinically feasible, and provided it is approved locally.
- 7. ECOG performance status 0-2.
- 8. Adequate organ function as defined by Screening laboratory values within the following parameters:
 - a. Absolute neutrophil count (ANC) $\geq 1.0 \times 10^3 / \mu L$ (off growth factors at least 72 h).
 - b. Platelet count $\geq 75 \times 10^3/\mu L$ without transfusion in the past 2 weeks.
 - c. Alanine aminotransferase (ALT), aspartate aminotransferase (AST), or gamma glutamyl transferase (GGT) \leq 2.5 \times the upper limit of normal (ULN) if there is no liver involvement; ALT or AST \leq 5 \times ULN if there is liver involvement.
 - d. Total bilirubin $\leq 1.5 \times \text{ULN}$ (patients with known Gilbert's syndrome may have a total bilirubin up to $\leq 3 \times \text{ULN}$ with direct bilirubin $\leq 1.5 \times \text{ULN}$).
 - e. Blood creatinine $\leq 3.0 \times \text{ULN}$ or calculated creatinine clearance $\geq 30 \text{ mL/min}$ by the Cockcroft-Gault equation.

- Note: A laboratory assessment may be repeated a maximum of two times during the Screening Period to confirm eligibility.
- 9. Negative beta-human chorionic gonadotropin (β-HCG) pregnancy test within 7 days prior to start of study drug for women of childbearing potential.
- 10. Women of childbearing potential must agree to use a highly effective method of contraception from the time of giving informed consent until at least 9.5 months after the last dose of camidanlumab tesirine. Men with female partners who are of childbearing potential must agree to use condom when sexually active or practice total abstinence from the time of giving informed consent until at least 6.5 months after the patient receives his last dose of camidanlumab tesirine.

Exclusion Criteria:

- 1. Previous treatment with camidanlumab tesirine.
- 2. Participation in another investigational interventional study. Being in follow-up of another investigational study is allowed.
- 3. Known history of hypersensitivity to or positive serum human ADA to a CD25 antibody.
- 4. Allogenic or autologous HSCT within 60 days prior to start of study drug.
- 5. Active graft-versus-host disease (GVHD), except for non-neurologic symptoms as a manifestation of mild (≤ Grade 1) chronic GVHD.
- 6. Post-HSCT lymphoproliferative disorders.

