Pregnancy test, if applicable	7.4.6	X	On C1D1,		on D1 of every 6 wks apart)	other cycle (max.	X^6	

	Protocol Section	Screening	Treatment Period			Follow-up Period (up to 3 years from EOT)		
(1 Cycle = 21 days)			Cycle 1 and	Cycle 1 and Cycle 2 (C1 and C2) C3 a			EOT	Every 12 weeks (wks)
Day (D)		-28 to −1	1	8	15	1		
12-lead ECG	7.4.7 Table 3	X	X (Pre, EOI, Post)	X	X	C3 and C4 (Pre, EOI), C5 then every other cycle (Pre)	X	
Premedication	6.7.1		D-1 to D2			D-1 to D2		
Camidanlumab tesirine administration	6.3		X			X		
PK sample	7.5.1 Table 4		X (Pre, EOI, Post)	X	X	C3 through C6 (Pre, EOI), then every cycle (Pre)	X	
ADA sample	7.5.2 Table 4		X (Pre)		X C1 only	C3 (Pre), then every other cycle (Pre)	X^7	
Soluble biomarkers	7.5.3.1 Table 5		X (Pre, Post)	X	X	C3 (Pre, EOI), then every other cycle (Pre)	X	
cfDNA samples (gDNA only at C1D1 and EOT)	7.5.3.1		X (Pre)			6 and 12 weeks postdose (with disease assessment)	X	X at disease progression
HRQoL ⁸	7.6		X			X	X	
Concomitant medications ⁹	6.8	Fro	From ICF signature date or D-14, whichever is earlier, until 30 days after last dose of study drug					
Adverse events	8	AE/SAE	AE/SAEs from ICF signature date until 30 days after last dose of study drug; thereafter, related SAEs only					
1 st New anticancer treatment	4.2.3						X	X
Survival	4.2.5						X	X

Abbreviations: ADA, anti-drug antibody; AE, adverse event; BP, blood pressure; cfDNA: circulating cell-free DNA; ECG, electrocardiogram; ECOG, Eastern Cooperative Oncology Group; EOI, end of infusion; EOT, end of treatment; HR, heart rate; gDNA, genomic DNA; HRQoL, health-related quality of life; ICF, informed consent form; PK, pharmacokinetics; post, postdose; pre, predose; RR, respiratory rate; SARS-CoV-2: respiratory syndrome coronavirus 2; SAE, serious adverse event; Temp, temperature; VZV, varicella zoster virus.

- Screening imaging must be performed within 4 weeks prior to C1D1 and the same assessment method should be used throughout the study. Week 6 imaging should be performed within 1 week prior to C3D1 and Week 12 imaging should be performed within 1 week prior to C5D1. All other imaging for disease assessment for patients on study drug should be performed within ±2 weeks of the scheduled timepoint. Disease assessments should be performed at the timepoints specified even if study drug dosing is delayed. If a scan has been performed within 6 weeks of EOT, it does not need to be repeated at EOT.

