Evaluate genetic alterations characterizing HL and their evolution upon camidanlumab tesirine treatment	 Detect HL alterations in plasma circulating free DNA (cfDNA) prior, during, and after camidanlumab tesirine treatment, including at disease progression Monitor residual disease prior to camidanlumab tesirine treatment and upon disease progression
Explore exposure-response relationships affecting safety and efficacy of camidanlumab tesirine	Relation between exposure (camidanlumab tesirine dose, PK metrics) and selected efficacy and safety endpoints
Explore correlations between clinical activity or safety of camidanlumab tesirine and tumor and/or blood biomarkers	Relation between tumor and/or blood biomarkers and selected efficacy and safety endpoints

4 Study Design

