5.1 Inclusion Criteria

- 1. Written informed consent must be obtained prior to any procedures.
- 2. Male or female patients aged 18 years or older.

For US sites only: Male or female patients aged 16 years or older.

- 3. Pathologic diagnosis of cHL.
- 4. Patients with relapsed or refractory cHL, who have received at least 3 prior lines of systemic therapy (or at least 2 prior lines in HSCT ineligible patients) including brentuximab vedotin and a checkpoint inhibitor approved for cHL (e.g., nivolumab or pembrolizumab).
 - Note 1: Receipt of HSCT to be included in the number of prior therapies needed to meet eligibility.
 - Note 2: The reason(s) for HSCT ineligibility must be documented in patient medical records/source documents and eCRF.
- 5. Measurable disease as defined by the 2014 Lugano Classification.
- 6. Availability of formalin-fixed paraffin-embedded (FFPE) tumor tissue block (or minimum 10 freshly cut unstained slides if block is not available).
 - Note 1: Any biopsy since initial diagnosis is acceptable, but if several samples are available, the most recent sample is preferred.
 - Note 2: If a sufficient amount of tissue is not available, a fresh biopsy may be taken, provided the procedure is not deemed high-risk and is clinically feasible, and provided it is approved locally.
- 7. Eastern Cooperative Oncology Group (ECOG) performance status 0-2.
- 8. Adequate organ function as defined by Screening laboratory values within the following parameters:
 - a. Absolute neutrophil count (ANC) $\geq 1.0 \times 10^3 / \mu L$ (off growth factors at least 72 h).
 - b. Platelet count $\geq 75 \times 10^3/\mu$ L without transfusion in the past 2 weeks.
 - c. ALT, AST, or GGT \leq 2.5 \times the upper limit of normal (ULN) if there is no liver involvement; ALT or AST \leq 5 \times ULN if there is liver involvement.
 - d. Total bilirubin $\leq 1.5 \times \text{ULN}$ (patients with known Gilbert's syndrome may have a total bilirubin up to $\leq 3 \times \text{ULN}$ with direct bilirubin $\leq 1.5 \times \text{ULN}$).
 - e. Blood creatinine $\leq 3.0 \times \text{ULN}$ or calculated creatinine clearance $\geq 30 \text{ mL/min}$ by the Cockcroft-Gault equation.

Note: A laboratory assessment may be repeated a maximum of two times during the Screening Period to confirm eligibility.

- 9. Negative beta-human chorionic gonadotropin (β-HCG) pregnancy test within 7 days prior to start of study drug for women of childbearing potential.

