5.2 Exclusion Criteria

- 1. Previous treatment with camidanlumab tesirine.
- 2. Participation in another investigational interventional study. Being in follow-up of another investigational study is allowed.
- 3. Known history of hypersensitivity to or positive serum human anti-drug antibody (ADA) to a CD25 antibody.
- 4. Allogenic or autologous HSCT within 60 days prior to start of study drug.
- 5. Active graft-versus-host disease (GVHD), except for non-neurologic symptoms as a manifestation of mild (≤ Grade 1) chronic GVHD.
- 6. Post-HSCT lymphoproliferative disorders.

- 7. Active second primary malignancy other than non-melanoma skin cancers, non-metastatic prostate cancer, in situ cervical cancer, ductal or lobular carcinoma in situ of the breast, or other malignancy that the Sponsor's medical monitor and Investigator agree and document should not be exclusionary.
- 8. History of symptomatic autoimmune disease (e.g., rheumatoid arthritis, systemic progressive sclerosis [scleroderma], systemic lupus erythematosus, Sjögren's syndrome, autoimmune vasculitis [e.g., Wegener's granulomatosis]) (subjects with vitiligo, type 1 diabetes mellitus, residual hypothyroidism, hypophysitis due to autoimmune condition only requiring hormone replacement may be enrolled).
- 9. History of neuropathy considered of autoimmune origin (e.g., polyradiculopathy including Guillain-Barré syndrome and myasthenia gravis) or other central nervous system autoimmune disease (e.g., poliomyelitis, multiple sclerosis).
- 10. History of recent infection (within 4 weeks of C1D1) considered to be caused by one of the following pathogens: HSV1, HSV2, VZV, EBV, CMV, measles, Influenza A, Zika virus, Chikungunya virus, mycoplasma pneumonia, *Campylobacter jejuni*, enterovirus D68, or severe acute respiratory syndrome coronavirus 2 (SARS-CoV-2).
 - Note: An influenza test and a pathogen-directed SARS-CoV-2 test (such as polymerase chain reaction [PCR]) are mandatory and must be negative before initiating study treatment (tests to be performed 3 days or less prior to dosing on C1D1; an additional 2 days are allowed in the event of logistical issues for receiving the results on time).
- 11. Patients who are carriers of human immunodeficiency (HIV) virus, hepatitis B virus (HBV), or hepatitis C virus (HCV), and require anti-viral therapy or prophylaxis.

 Note: Serology testing is mandatory for patients with unknown status.

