7.5.3 Biomarkers

7.5.3.1 Blood Samples for Biomarkers

Blood samples for biomarkers analyses will be collected as per SoE (Table 1) and a more detailed presentation of soluble markers timepoints is provided in Table 5.

Please refer to the laboratory manual for detailed instructions regarding specimen handling and shipment.

Soluble Biomarkers: Up to 6 mL of blood for the quantification of immunologically relevant biomarkers (e.g., IL-2, IL-6, IL-8, IL-10, IFN γ , TNF α , sCD25, CCL17) will be taken at multiple timepoints. This will include analyses of biomarkers that may be predictive of or associated with GBS (at a minimum on C1D1 and C3D1 predose).

cfDNA/gDNA: Up to 30 mL of whole blood will be taken at multiple timepoints for investigating genetic alterations characterizing Hodgkin lymphoma in cfDNA. gDNA will be analyzed to confirm the somatic origin of the genetic alterations and will be measured at predose C1D1 and EOT only.

^{*} Postdose timepoint is counted from start of infusion.

 Table 5
 Sampling Schedule for Soluble Biomarkers

Cycle	Day	Timepoint (window)
C1	D1	Predose (preferably within 2 h prior to start of infusion)
		Postdose* 4 h (± 10 min)
	D8	Postdose* 168 h (± 48 h)
	D15	Postdose* 336 h (± 48 h)
C2	D1	Predose (within 2 h prior to start of infusion)
		Postdose* 4 h (± 10 min)
	D8	Postdose* 168 h (± 48 h)
	D15	Postdose* 336 h (± 48 h)
C3	D1	Predose (within 2 h prior to start of infusion)
		EOI (within 10 min prior to EOI)
C5, C7,	D1	Predose (within 2 h prior to start of infusion)
every other cycle		
ЕОТ		At any time during visit day
Follow-up		-
Unscheduled		Any time (if applicable, together with PK sample)

Abbreviations: EOT, end of treatment; PK, pharmacokinetics.

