4.5 Cancer History and Medications History

Cancer history will be presented for the all-treated population. Cancer history will include the following variables:

- Duration since diagnosis
- Classical Hodgkin lymphoma subtype (nodular sclerosis classical Hodgkin lymphoma [cHL], lymphocyte-rich cHL, mixed cellularity cHL, lymphocyte-depleted cHL, and other)
- Stage of disease at study entry (Stage I, II, III, IV; constitutional symptoms A, B; Subtype E, X, S)
- Cytogenetic analysis
- Immunophenotypic analysis (results available yes; CD15, CD30, PAX5, CD3, CD20, CD45, CD79a, BCL6, etc.)

Prior anticancer procedure or therapy will include the following variables:

- Number of lines of therapy/regimens per patient
- Response to the first line and/or most recent line of prior systematic therapy
- Any prior radiotherapy for the current malignancy (yes, no)
- Any prior surgery for the current malignancy (yes, no)
- Reason for stopping therapy (progression, lack of response, toxicity, completed treatment, partial or complete remission, other)
- Best response (complete response [CR], partial response [PR], stable disease [SD], progressive disease [PD], not evaluable [NE])
- Any prior stem cell transplant (yes, no)
- Primary reason for transplant ineligibility prior to entering the study
- Type of transplant (allogenic, autologous, both, other)

Medical and cancer history data will be listed. Results of cytogenetic analysis and immunophenotypic analysis will be listed. Tumor tissue biopsy collection will not be listed, but will be contained in datasets.

Prior anticancer surgery, radiotherapy, systemic therapy, and stem cell transplant data will be listed.

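### Blood gDNA cannot by itself confirm somatic origin of cfDNA alterations in patients with a prior allogeneic transplant, and the plan has no rule for them

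*Protocol*

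**What the plan says.** **Sampling and purpose.** Protocol Section 7.5.3.1 states: "Up to 30 mL of whole blood will be taken at multiple timepoints for investigating genetic alterations characterizing Hodgkin lymphoma in cfDNA". On the comparator it states: "gDNA will be analyzed to confirm the somatic origin of the genetic alterations". The row in Table 1 is headed "cfDNA samples (gDNA only at C1D1 and EOT", and Section 7.5.3.1 specifies that the C1D1 sample is predose. Neither document names a non-haematopoietic reference sample.

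**Eligibility.** Exclusion criterion 4 (Synopsis and Section 5.2) reads "Allogenic or autologous HSCT within 60 days prior to start of study drug". Exclusion criterion 5 bars active graft-versus-host disease "except for non-neurologic symptoms as a manifestation of mild (≤ Grade 1) chronic GVHD", so patients living with an allogeneic graft are foreseen. A note to inclusion criterion 4 (Section 5.1) adds "Receipt of HSCT to be included in the number of prior therapies needed to meet eligibility".

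**Data already collected.** SAP Section 4.5 tabulates "Type of transplant (allogenic, autologous, both, other" among the prior-therapy variables. For transplants after study drug, Protocol Section 7.3 has the type of HSCT recorded in the eCRF.

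**Endpoints.** Table 2 lists as exploratory "Detect HL alterations in plasma circulating free DNA (cfDNA) prior, during, and after camidanlumab tesirine treatment, including at disease progression", together with monitoring of residual disease before treatment and at progression, and the relation of blood biomarkers to efficacy and safety. The SAP repeats the exploratory objectives but has no cfDNA analysis section. Protocol Section 9.11 allows exploratory results to be reported separately.

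**The concern.** Confirming somatic origin from blood gDNA relies on blood cells carrying the patient's inherited genome. After an allogeneic transplant they carry the donor's, wholly or in large part. Tumour and other non-blood tissue still carry the patient's and still shed DNA into plasma. This is general biology, not a figure from the documents.

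In such a patient the comparison can fail without any laboratory error. An inherited patient variant missing from the donor is seen in cfDNA, is not seen in gDNA, and looks acquired. For a patient transplanted before entry, both gDNA timepoints fall after the transplant, so the EOT sample repeats the same reference and does not expose the problem.

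At stake is the list of HL alterations before, during and after treatment, the residual-disease readings, and any correlation built on them. The error is systematic and sits in a subgroup defined by prior treatment, so adding patients does not average it out.

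**Working it through.** The documents give no figure on this point, so there is none to reproduce. The check is a reading of the passages side by side, followed by illustrations that rest on stated assumptions.

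**1. Do the passages combine as claimed?**
- Comparator: blood gDNA at C1D1 predose and EOT (Table 1, Section 7.5.3.1).
- Population: allogeneic HSCT more than 60 days before first dose is allowed (exclusion 4), and mild chronic GVHD is tolerated (exclusion 5).
- Special handling: none in either document. There is no exclusion from the cfDNA analysis, second reference or chimerism test.
- Tumour tissue (Section 7.5.3.2) is collected for predictive markers and is not designated as a germline reference.

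The comparison therefore applies, as written, to patients in whom its premise does not hold.

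**2. What would a falsely somatic variant look like?** Let f be the patient's share of plasma cfDNA and c the donor share of blood cells. For a heterozygous patient variant that the donor lacks:
- allele fraction in cfDNA = f/2. For assumed f = 5%, 10%, 20%, 30% this is 2.5%, 5%, 10%, 15%.
- allele fraction in blood gDNA = (1 − c)/2. For c = 100% this is 0; for c = 95% it is 2.5%; for c = 90% it is 5%.

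At full chimerism the variant is present in cfDNA and absent from gDNA. With mixed chimerism a low signal may be visible in gDNA, and the effect weakens.

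**3. How often does the donor lack a variant?** Let q be the allele frequency and p = 1 − q.
- Rare heterozygous patient variant, unrelated donor: (1 − q)². For assumed q = 0.1%, 1%, 5% this is 99.8%, 98.0%, 90.3%. For a sibling or haploidentical donor it is about 50%.
- Common polymorphism, chance that the patient carries it and the donor does not (Hardy-Weinberg), at q = 0.1, 0.3, 0.5:
  - unrelated donor: (1 − p²)p² = 0.154, 0.250, 0.188;
  - full sibling: p² − (0.25p² + 0.5p³ + 0.25p⁴) = 0.079, 0.136, 0.109.

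A population-frequency filter would remove most common polymorphisms. The rare variants are the ones likely to survive it.

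**4. How many patients?** The share with a prior allogeneic transplant is not stated. For an assumed 5% to 30% of about 100 patients, it is 5 to 30 patients.

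**5. Would dropping blood gDNA cure it?** No. Donor blood cells also shed into plasma. A heterozygous donor variant that the patient lacks would appear in cfDNA at (1 − f)/2, which is 47.5% at f = 5% and 35% at f = 30%. Without blood gDNA to identify it, it too could be read as somatic. Both references are needed.

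**6. On-study transplants.** The EOT visit is to come before any new anticancer treatment (Section 4.2.3), so both gDNA samples precede a later transplant. Disease assessment continues after HSCT (Section 7.3) and cfDNA is drawn at progression in follow-up (Table 1). In that sample, variants from a new donor could look like newly acquired alterations.

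**The case against.** The strongest reply is that no calling algorithm is written down. Section 7.5.3.1 gives only the purpose of gDNA; reading absence from gDNA as somatic is an inference. Population-variant filters or another reference may sit in documents not supplied. Exploratory results may be reported separately, and no confirmatory analysis depends on them.

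Much of this stands. A reader might infer that every inherited variant in these patients will be confirmed as somatic. The documents do not support that: the outcome depends on the pipeline, on the donor lacking the variant, and on chimerism. A reader might also multiply the common-polymorphism probabilities by a panel size to get false calls per patient. No panel is described, and common polymorphisms are the easiest to filter, so such a count has no basis here.

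A third tempting inference is that residual disease would appear present in complete responders. Table 2 words the residual-disease endpoint for before treatment and at progression, not for remission. Only the separate endpoint on detecting HL alterations uses the week 6 and week 12 samples. Variants that persist unchanged would not mimic clearance or new alterations there, although f/2 moves if the patient's share of cfDNA moves.

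A fourth is that shipped tumour tissue could replace blood gDNA. Tissue carries the somatic alterations being sought, and Section 7.5.3.2 prefers the most recent sample, which may be post-transplant. Step 5 shows that discarding blood gDNA creates the mirror error.

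The reply does not restore the comparison. It rests on the patient's own genome being in the blood, eligibility admits patients in whom it is not, and nothing in either document handles them. The laboratory manual is cited in Section 7.5.3.1 only for specimen handling and shipment.

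**Conclusion.** The point holds in a limited form. For patients with an allogeneic transplant more than 60 days before first dose, blood gDNA alone cannot confirm that a cfDNA alteration is somatic, because an inherited patient variant that the donor lacks can pass the check. Autologous recipients are not affected.

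The reach is confined to the exploratory cfDNA and residual-disease endpoints and their biomarker correlations. The primary response analysis, its power, the other efficacy endpoints and safety are untouched. The size is unknown: the 5 to 30 patients and the probabilities above rest on assumed shares and allele frequencies, and they illustrate the mechanism without estimating the number of false calls. The conclusion itself needs only substantial donor chimerism in blood and the absence of a second reference.

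**What to change.** In Section 7.5.3.1 and in the cfDNA analysis plan, add one rule for patients whose prior transplant type (SAP Section 4.5) is allogenic or both:

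- Do not treat blood gDNA alone as confirming somatic origin.
- Leave these patients out of the somatic-origin and residual-disease summaries, and list their results separately.
- Keep their blood gDNA, which is needed to remove donor variants.
- Include a patient in the summaries only if a recipient germline reference already exists in addition to blood gDNA. Tumour tissue alone does not serve as that reference.
- Apply the same rule to cfDNA drawn after an on-study allogeneic HSCT, using the transplant type recorded under Section 7.3. In a patient with no earlier allograft, the study's gDNA is then the recipient reference and the donor's is the one missing.

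The rule needs no new sample, visit or eCRF field. Its cost is that a few patients, or single samples, become non-evaluable for an exploratory endpoint.

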1.1 Targeting CD25-positive Tumor Cells in Hodgkin Lymphoma

Hodgkin lymphoma (HL) is a lymphoid malignancy of B-cell origin, which is classified into either nodular lymphocyte predominant Hodgkin lymphoma or classical Hodgkin lymphoma (cHL). The latter accounts for 95% of all HLs and is addressed by this protocol (Fields, 2017). Thus, for convenience, cHL/HL will be used interchangeably.

The epidemiology of HL is characterized by bimodal incidence (15-34 years and 55+ years). Therapeutic advances have resulted in durable remission rates of 60-80%. However, there is an unmet medical need for patients' refractory or relapsing from current treatments. Since many of these patients are of young age, the potential loss of life years is significant (Mehta-Shah, 2018; Fields, 2017; Glimelius, 2017).

Brentuximab vedotin as a single agent and checkpoint inhibitors have been approved for use in the relapsed setting, and thus patients coming onto this trial should have received both of these therapies. However, once these therapies fail or are not tolerated, treatment options are limited (Mehta-Shah, 2018; Mottok, 2018; Fields, 2017; Glimelius, 2017). It is in this setting where camidanlumab tesirine, an antibody-drug conjugate that is directed against human cluster of differentiation (CD25), will be clinically tested.

The CD25 is the alpha-chain of the interleukin (IL)-2 receptor and as such expressed on the cell surface of a number of normal cells of the immune system as well as malignant cells (Flynn, 2017).

[figure not shown]
The presence of CD25-positive cells in hematologic malignancies and the relationship between increased CD25 expression and poor prognosis raises the possibility of using an anti-CD25 antibody to deliver a cytotoxin to these cells in patients. Hematologic malignancies expressing CD25 include adult T-cell leukemia (Waldmann, 1995), hairy cell leukemia (Shao, 2013), anaplastic large cell lymphoma (Strauchen, 1987), cutaneous T-cell lymphoma (Olsen, 2001; Prince, 2010), chronic lymphocytic leukemia (Shvidel, 2012), HL (Schnell, 1998), follicular lymphoma (Fujiwara, 2013a), diffuse large B-cell lymphoma (Fujiwara, 2013b), acute myeloid leukemia (Cerny, 2013), acute lymphocytic leukemia (Geng, 2012), and systemic mastocytosis (Lim, 2009). Expression of CD25 is positive (≥ 20% tumor cells) in approximately 58% to 78% of HL (Strauchen, 1987; LeMaistre, 1998).

